6.6.1 Development of quality of care indicators for AD

Firstly, an extensive, systematic literature review, including national and international guidelines on atopic dermatitis, was performed in order to identify potential quality indicators. This systematic literature review resulted in 74 indicators.

In the second stage, an expert committee consisting of 10 members was formed. All members of the expert committee had previously been involved in the development of the S2 guideline on the treatment of AD. The members of this expert committee extracted the final quality indicators in a modified Delphi consensus process. The expert condensed the 74 indicators of quality of care indicators identified in stage 1 to a set of 24 quantifiable non-redundant key indicators of clinical relevance.

A second Delphi survey resulted in 15 key indicators. Moreover, the results were discussed in a smaller expert group including physicians, statisticians, methodologists and patients. In the final round, the 10 members of the expert committee agreed on the 12 proposed quality indicators (table 2):

Area	Indicator	Condition
	AD provocation factors	The patient has been asked for provocation factors
History	Patient's personal history of atopy	The patient has been asked about factors associated with atopy, e.g. allergic rhinitis, allergic asthma, family history
Diagnostics	Hanifin and Rajka criteria	The criteria were assessed
Diagnostics	RAST (=Phadiatop) test	RAST testing was performed
	Regular performed skin care	Regular skin care was applied
Treatment	Corticocosteroids and/or topical immunomodulators	Topical steroids or topical immunomodulators were used
	Antiseptics for impetiginisation	In case of impetiginisation antiseptics were used
	Avoidance of provocation factors	Provocation factors were avoided
	Decontamination of house dust if sensitized to dust mites	Measures against house dust mites were taken
Prevention	Avoidance of smoking at home	Smoking was avoided at home
	Individual counselling on prevention	The patient has participated in individual counselling on prevention factors
	Taking part in patient education classes	The patient has taken part in at least on patient education program

	Table 2: Process q	uality indicators	derived from ex	pert consensus	based on guid	deline
--	--------------------	-------------------	-----------------	----------------	---------------	--------

Seven (eight only if patients sensitized to dust mites were analyzed) applicable key process indicators were evaluated in AtopicHealth1 on n = 1,678 patients in 2010.

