5.2 Goal and benefit of the study

The aim of the present planned study "AtopicHealth2" is the generation of up-to-date scientific data concerning the quality of care for atopic dermatitis in Germany. A particular focus lies upon the description of ongoing therapies, quality of life and individual treatment needs and benefits from the patient's perspective. Adult patients with all levels of severity and age groups are included. The Study is methodologically and contend-relatedly tied to the first national health care evaluation study AtopicHealth1. With these data, concerns about care from the patient-side as well as supply gaps can be characterized further and measures can be reached on different levels.

The planned study represents an outstanding occurrence in German health services research, as it is a continuation of the study AtopicHealth1, conducted in 2010, capturing the standard of care for atopic dermatitis from the patient's perspective with representative data, allowing comparisons over a period of more than 6 years. The results of the study intend to serve the scientific analysis of the current supply of care with topical therapy and systemic drugs and are applicable in the argumentation towards prescribers, users, cost bearers and decision-makers in health care policy ("health economic positioning"). Furthermore, the data serves acquiring knowledge regarding the preferences and application behavior of patients with atopic dermatitis. Multiple usage of the generated data is strived at.

Thus the study shows several significant benefits for the patients and supplying physicians:

- 1. The nationwide survey concerning the subjective burden of disease allows assessment of patient "distress" and the need for care concerning atopic dermatitis.
- 2. As an inventory control of the current care, the study enables an acquisition of the existing supply gap with solid data.
- 3. Due to profiling of the "poorly cared-for patient" and his or her needs, the study facilitates future care provision planning.
- 4. The recorded predictors of "poor care" are requirements for the targeted dismantling of "care barriers" to date, a not yet introduced strategy in Germany.
- 5. Due to the acquisition of quality indicators and benefit assessment from the patient's perspective, the study allows a profound analysis of the benefit as perceived by the patient of the hitherto appointed types of therapy.

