6.2 Objectives

Concerning the current study, the following questions will be clarified:

- How high is the subjective burden of disease of patients with atopic dermatitis in 2016/2017 in Germany?
- 2. What are the patient-specific needs in the course of medical care?
- 3. How is the quality of care for different levels of severity and therapeutic groups of the disease?
- 4. What kind of quality does the care measured via guideline compliant quality indicators and single items demonstrate compared to 2010?
- 5. How is the benefit of the medical services assessed from the patient's perspective?
- 6. To what extent are restrictions of compliance perceived from the patient's perspective and how are these explained?
- 7. To what extent is there an undersupply, particularly regarding treatment with systemic drugs?
- 8. Which predictors can be found for a proficient/poor care for atopic dermatitis patients?
- 9. How high are the costs-of-illness caused by atopic dermatitis and which predictors can be found?
- 10. Which impact does atopic dermatitis have on workability?

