6.5 Project development

The project consists of the following steps:

- 1. Conception
 - a. Information to the boards of the German dermatology societies DDG and BVDD
 - b. Cooperation agreements
 - c. Obtainment of ethics vote
- 2. Planning
 - a. Systematic literature research on national and international standards on diagnosis and treatment of atopic dermatitis following Cochrane criteria
 - b. Refinement of definitions for core concepts of outcomes, e.g. quality of care, status of "high need" and status of "underprovision of health".
 - c. Application of quality of care indicators that were developed based on "AtopicHealth1" by an expert committee consisting of 10 members:
 - i. Process indicators (derived from expert consensus based on guideline)
 - ii. Outcomes indicators (derived from expert consensus process)
 - d. Biometric planning
 - e. Adaptation and final versions of study forms and questionnaires
- 3. Study conductance
 - a. Recruitment of centres
 - b. Data collection in the centres
 - c. Data entry and -management
 - d. Determination of assessed cost parameters
- 4. Data analysis and statistical evaluation
- 5. Final report
- 6. Publications

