6.6 Outcomes

If obtainable from patient details, the outcome-parameters are selected, if possible, in a large consensus with the international standards as well as the preliminary publications of the HOME-Initiative (Schmitt J et al. and Augustin M et al). The following target parameters are intended:

1) Description of the level of severity

- Clinical: SCORAD (Darsow et al. 2005), Body Surface Area (grid for recording) (Wallace 1951); optionally EASI (to be discussed with sponsor)
- Dermatology Quality of Life: DLQI (Finlay und Khan 1994), EQ VAS (generic health questionnaire); (EuroQol--a new facility for the measurement of health-related quality of life 1990; Schulenburg vd et al. 1998)

2) Description of the health care situation and quality of care

- Process: quality: "Health care-index" from 12 indicators of process quality (see below, 6.6.1)
- Outcomes: quality: based on a selected number of single outcomes, e.g. DLQI, PBI, SCORAD
- Data regarding the present supply chain

3) Presentation of patient benefit of the ongoing therapy and compliance

- Patient benefit Index PBI (Augustin et al. 2009; Blome et al. 2009)
- Compliance Scales (adapted from AtopicHealth1)

4.) Health economic outcomes

- Direct costs (treatment costs, out-of-pocket costs): EKK (adapted from "PsoHealth3")
- Indirect costs incl. workability: EKK (adapted from PsoHealth3)
- Presenteism and absenteeism: Work Productivity and Activity Impairment (WPAI) (Reilly et al. 1993)

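### Four of the 12 process-quality indicators record patient or household behaviour, so the Health care-index alone cannot separate care delivered from what happens at home

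*Protocol*

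**What the plan says.** Protocol 6.6, point 2, describes quality of care by three things: a process measure, outcome quality (single outcomes such as DLQI, PBI and SCORAD) and supply-chain data. The process measure is the Health care-index, formed "from 12 indicators of process quality". Section 6.5, step 2c, labels the items "Process indicators (derived from expert consensus based on guideline".

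Table 2 in 6.6.1 gives a condition for each indicator. Some conditions describe an act of the provider: the patient was asked, criteria were assessed, a test was done. Four describe conduct of the patient or household:

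- "Regular skin care was applied"
- "Provocation factors were avoided"
- measures taken against house dust mites, for patients sensitized to them
- "Smoking was avoided at home"

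None of the four is worded as advice given or a measure prescribed.

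The aims to which such an index could contribute are objective 8 in 6.2 ("Which predictors can be found for a proficient/poor care for atopic dermatitis patients"), the profile of the poorly served patient and the removal of barriers to care (5.2, benefits 3 and 4), and regional differences (5.2, benefit 7). Compliance is a separate outcome (6.6, point 3) and a separate objective (6.2, no. 6).

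**The concern.** The smoking item shows the difficulty most clearly. A patient from a non-smoking household meets it with no care given. A fully counselled patient who lives with a smoker fails it. The item does not record whether the practice did anything, yet it counts towards process quality.

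What is at stake is the meaning of a predictor of poor care. If age, education or region goes together with smoking at home or with self-care habits, it can be associated with a low index even where practices delivered the same care. A reader who wants to remove barriers to care would then look to the practices for a cause that may lie in the household. The index is the only process-quality measure that 6.6 lists, so no second process measure would reveal this.

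**Working it through.** **Count.** Table 2 has 2 history rows, 2 diagnostics rows and 8 treatment or prevention rows: 2 + 2 + 8 = 12. This reproduces the stated 12.

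**Classification by the wording of each condition.**

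- Patient or household conduct (4): skin care, avoidance of provocation factors, mite measures, smoking at home.
- Provider and patient together (3): topical steroids or immunomodulators used, counselling participated in, education classes attended.
- Mainly provider (5): asked about provocation factors, asked about atopy, Hanifin and Rajka criteria, RAST, antiseptics for impetiginisation. The antiseptic item is also worded as use, so it could be moved to the middle group. The argument does not depend on that.

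**Share of items.** Two items are conditional: mite measures (sensitized patients) and antiseptics (impetiginisation). If an item that does not apply leaves the denominator, which is an assumption, the behaviour share is:

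- neither applies: 3/10 = 30%
- impetiginisation only: 3/11 = 27%
- mite sensitization only: 4/11 = 36%
- both apply: 4/12 = 33%

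Adding the three mixed items to the full list gives (4 + 3)/12 = 58% as an upper count of items that depend at least partly on the patient.

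**Effect on the score.** This step assumes equal weights, a 0–100 scale and all 12 items applicable. The protocol states no scoring or weighting rule.

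- Two patients with identical results on the other eight items can differ by up to 4/12 × 100 = 33 points. If neither conditional item applies, the figure is 3/10 × 100 = 30 points.
- One item is worth 100/12 = 8.33 points. A 10-percentage-point group difference in smoking at home shifts the group mean by 8.33 × 0.10 = 0.83 points; a 20-point difference shifts it by 1.67 points.
- A 10-percentage-point difference on all four items shifts the mean by 4 × 8.33 × 0.10 = 3.33 points.

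**Could such shifts be detected?** Section 6.7 expects high power at n = 1,500, in many analyses even for small effects, but gives no alpha, effect size or group split, so its figure cannot be reproduced. For illustration, assume two groups of 750, two-sided alpha 0.05, an index SD of 10 to 20 points and no clustering within sites:

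- shift 1.67 points: d = 1.67/20 to 1.67/10 = 0.08 to 0.17, power 0.37 to 0.90
- shift 3.33 points: d = 3.33/20 to 3.33/10 = 0.17 to 0.33, power 0.90 to 1.00

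The SD, the split and the behaviour differences are assumptions. Unequal groups or clustering would lower these powers.

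**The case against.** The strongest reply is that the composition was deliberate. A literature review gave 74 candidates, which expert rounds reduced to 24, 15 and then 12, with statisticians, methodologists and patients joining the discussion. The synopsis sets out to describe care from the patient's as well as the physician's side, and 5.2, benefit 6, looks for patient-side predictors. Guideline care as actually realised, including skin care carried out and triggers avoided, fits those aims. This stands: the list is not an error, and the consensus index should remain. But agreement on clinical relevance does not make the total a measure of provision alone.

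Three further objections also stand.

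- A reader might infer that the predictor and regional analyses are confounded. The protocol names the index as the outcome of neither; it lists other quality measures, and 6.5, step 2b, leaves the definition of quality of care to be refined. Distortion also needs behaviour to differ between the groups compared, and the protocol has no data on that.
- A reader might infer that the same behaviour is counted twice, as process quality and as compliance. The content of the Compliance Scales is not shown, so overlap is possible but not established.
- Removing the four items does not give a pure provider score, because three of the remaining eight still depend on patient use or attendance.

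Section 6.7 also asks for effect sizes beside significance tests, and objective 4 looks at single items. Both help against over-reading a small shift. Neither shows whether the shift came from the practice or from the home.

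**Conclusion.** The point holds as a limit on interpretation. Four of the 12 process indicators, or 27% to 36% of applicable items, turn on patient or household behaviour. Where the index is used for objective 8 or for regional differences, it cannot by itself tell under-provision from behaviour.

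A reader might also take the third of items as a third of the score, or the 33-point gap as an expected bias. The first needs equal weights. The second needs in addition that both conditional items apply, and it is a maximum between two individuals. Group shifts under the illustrated differences are about 1 to 3 points on a 100-point scale. The actual size cannot be known from the protocol.

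**What to change.** In 6.6, keep the 12-item consensus index as the main figure and add two scores from the same items: (a) the index without the four behaviour items, and (b) those four items as a separate patient-behaviour score. Where the index is used for objective 8 or the regional comparison, repeat the analysis on (a) and attribute a predictor to care provision only if it persists there. State that three items left in (a), namely topicals used, counselling participated in and education classes attended, depend on both provider and patient. State also how items are weighted and how non-applicable items are handled.

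The cost is about one paragraph and a second set of analyses, with no new data. The reduced score has fewer items and no consensus backing of its own, which is why it should stand beside the full index and not replace it. This is a cheap improvement to the plan, not a correction of an error.

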6.7 Sample size consideration

Due to the sample size of n=1,500 a high power up to 100% can be expected with regard to the relevant significance tests – in many analyses even for small effects. Hence it is essential to complement significance tests whenever possible with effect size measurements.

6.8 Data management

The arrival of each questionnaire will be documented by the study center. All the data will be copied from the original questionnaires and entered manually in Excel databases by trained and experienced data managers. To detect systematic errors of data entry the first 100 data sets will be entered twice in two different databases by independent managers. Afterwards, the two records of the same patients will be compared and in case of discrepancy an independent data manager will determine the correct entry using the original questionnaires. Furthermore, after importing the whole data set to SPSS it will be analyzed for plausibility by application of appropriate algorithms. Implausible data will be corrected or defined as missing values.

Free text entries about clinical characteristics and treatment will be checked and categorized by a physician. Data regarding health economic outcomes will be checked, categorized and translated into concrete costs by an expert in health economy prior to further analysis.

6.9 Statististical analysis

All data will be analysed with descriptive statistics and specified in terms of statistical standard values (absolute and percentage frequencies for categorical data; min, max, mean, standard deviation, median for continuous data). Further statistical analyses will be performed according to the study questions. In particular, the outcomes of different subgroups will be compared and predictors for specific outcomes will be determined by application of adequate significance tests. Data analyses will be conducted by means of IBM SPSS Statistics for Windows, Version 23 (IBM Corp., Armonk, NY, USA).

6.10 Quality assurance

The study will be conducted following the criteria for Good Epidemiological Practice. CVderm was certified in accordance with DIN ISO 9001 in 2008 and was re-certified in 2013. Furthermore, CVderm follows its own standard operating procedures.

6.11 Adverse Events

In the course of this scientific project, no specific data on the safety of medical products will be collected. However, the study participants will be reminded about their obligation to submit any important safety data in the usual German procedure (Nebenwirkungsmeldungen an das BfArM oder die Arzneimittelkommission der Deutschen Ärzteschaft).

6.12 Data protection and ethics

Before implementing this study, the protocol, the questionnaires, the proposed informed consent and the patient information gets reviewed by the Hamburg Physician Chamber Ethics Committee.

The study (including the participating dermatologists) follows the current legal requirements for data protection. Patients will only be included as study participants if they have given their informed consent in a written form to their dermatologists. For this purpose the CVderm provides written information to patients and a declaration of consent for the participating dermatological centers. For the study interviews in the dermatology centers the dermatologist is responsible solely. The questionnaires will be pseudonymised (encrypted with a numerical code so that only the staff of the recruiting site is able to allocate personal patient data by using a so called key list).

The participating centers make sure to save the original versions of the patient agreement as w ell as the corresponding key list for ten years beyond the end of the study. The pseudonymised questionnaires will be processed to the statistical analysis unit of CVderm. This way, it is not possible for the statistical analysers to identify an individual person. Pseudonymised questionnaires will be archived as paper

forms or on storage media at the University Medical Center Hamburg-Eppendorf for 10 years. If necessary inspection of the study documents can be granted to regional authorities.

All patients are entitled to ask for information on individual study related data in the respective dermatological center. The latter can receive this data from the study center by transferring the numerical code of this individual patient.

6.13 Publications

The data will be reported in an internal study report. This will contain study objectives, methods and results. Furthermore, results of the study will be published in international journals under the authorship of all significantly contributing scientists and will be presented at conferences as oral or poster presentations.

7 Timeline

Exact timelines depend on the starting time and will be provided after finalizing the study contract. Some periods may be overlapping.

Study preparation, including obtainment of ethics vote	10 to 16 weeks	
Centre recruitments	8 weeks	
Overall recruitment period	52 weeks	
First patient inclusion	tbd	
Last patient inclusion	tbd	
Interims report	18 weeks after first patient in	
Final data management period (after last patient out)	4-12 weeks	
Determination of assessed cost parameters	4-8 weeks	
Data analysis	4-8 weeks	
Final report	4 weeks	
First publication	After submission of final report	

This project will be supported by an unrestricted grant from Sanofi Aventis GmbH Deutschland. The supporting body does not have any responsibilities in the study. The study planning, operation and publication will be conducted independently from any third party support.

8 References

Augustin, Matthias; Franzke, Nadine; Beikert, Florian C.; Stadler, Rudolf; Reusch, Michael; Schmitt, Jochen; Schafer, Ines (2013): Allergies in Germany -- prevalence and perception by the public. In: *Journal der Deutschen Dermatologischen Gesellschaft = Journal of the German Society of Dermatology: JDDG* 11 (6), S. 514–520. DOI: 10.1111/j.1610-0387.2012.08049.x.

Augustin, Matthias; Radtke, Marc A.; Glaeske, Gerd; Reich, Kristian; Christophers, Enno; Schaefer, Ines; Jacobi, Arnd (2015): Epidemiology and Comorbidity in Children with Psoriasis and Atopic Eczema. In: *Dermatology (Basel, Switzerland)* 231 (1), S. 35–40. DOI: 10.1159/000381913.

Augustin, Matthias; Radtke, Marc A.; Zschocke, Ina; Blome, Christine; Behechtnejad, Julia; Schafer, Ines et al. (2009): The patient benefit index: a novel approach in patient-defined outcomes measurement for skin diseases. In: *Archives of dermatological research* 301 (8), S. 561–571. DOI: 10.1007/s00403-009-0928-8.

Beikert, F. C.; Langenbruch, A. K.; Radtke, M. A.; Kornek, T.; Purwins, S.; Augustin, M. (2014): Willingness to pay and quality of life in patients with atopic dermatitis. In: *Archives of dermatological research* 306 (3), S. 279–286. DOI: 10.1007/s00403-013-1402-1.

